**A Mechanistic Perspective on Post-Activation Performance
Enhancement Responsiveness: A Randomized Controlled
Study of Acute Changes in Muscle Architecture, Contractile
Property Kinetics, and Muscle Excitability**

NCT06982937

18.05.2025

Objectives and endpoints.

The primary objective is to test whether a heavy conditioning activity (CA; one set of 2–3 repetitions at ~90% 1RM) produces post-activation performance enhancement (PAPE) in countermovement jump (CMJ) height compared with a control treadmill warm-up within the 4–12 min window after the intervention. The analysis does not assume *a priori* when the maximal effect occurs; instead, the minute of maximal between-group difference (denoted T^*) will be identified empirically. The primary endpoint is the change in CMJ height from baseline (ΔCMJ) at post-intervention time points (4, 6, 8, 10, 12 min). Secondary endpoints include the time-course of ΔCMJ within the experimental group (EXP), individual responder status at each time point, and the associations between neuromuscular phenotype—estimated as %MHC-I from tensiomyography (TMG)—and the magnitude, timing, and likelihood of response. Ultrasound (USG) morphology (muscle thickness, pennation angle, derived fascicle length) will be analysed in parallel to performance endpoints. Electromyography (EMG), where available, will be treated analogously to USG/TMG (see below).

Data handling and derived variables.

At each time point, CMJ height is the mean of three trials; ΔCMJ and percentage change (% ΔCMJ) will be computed relative to baseline. Individual response is classified using MDC. USG outcomes will be averaged across three images; fascicle length is calculated as thickness divided by the sine of pennation angle (degrees converted to radians). TMG-based %MHC-I is estimated from delay, contraction, and half-relaxation times using the published multivariable model; TMG amplitudes and time constants may also be expressed as Δ or % Δ . If EMG is collected, signals will be band-pass filtered, rectified, quantified with 50-ms RMS, normalized (to MVC or M-wave), and summarized over task-relevant phases; % Δ at 4–12 min is computed analogously. Values >3.5 SD from group-time means will be flagged; primary analyses include all data, with winsorized sensitivity checks reported only if inferences change. Missing data will be not imputed for the primary analysis; mixed-effects models accommodate missingness assuming MAR.

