Primary analysis and identification of the peak time (T^*).

The confirmatory analysis uses a RM-ANOVA with ΔCMJ as the outcome, Group (EXP vs CON), Time (time effect: 4, 6, 8, 10, 12 min), and Group \times Time. If the interaction is significant, we estimate adjusted between-group contrasts at each minute with Bonferroni correction across the five time points. T^* is defined as the minute showing the largest positive EXP–CON difference in estimated marginal means (EMMs) with the smallest p-value. We report the EMM difference at T^* (95% CI) and effect size (d’Cohen). Greenhouse–Geisser correction if needed.

Within-group time-course and kinetics.

To describe the temporal profile without prespecifying a target minute, we analyse ΔCMJ across time within EXP using a one-way repeated-measures ANOVA (or LMM if assumptions are violated), followed by Bonferroni-adjusted pairwise EMMs to locate the within-group peak. To characterise response timing at the individual level, we model time to first and time to peak response (4–12 min) using Kaplan–Meier curves with censoring at 12 min, compare strata by log-rank tests, and fit Cox proportional-hazards models to estimate hazard ratios (HR, 95% CI) and concordance (C-index). This kinetics framework provides an assumption-light estimate of when athletes typically express PAPE.

Responder analyses and discrimination.

Responder distributions (Positive/neutral/adverse) will be compared between EXP and CON at each minute using likelihood χ^2 test. For mechanistic discrimination at specific minutes (including T^* once identified), we fit logistic models with %MHC-I as a continuous predictor and report ORs (95% CI),

Nagelkerke R², AIC, Hosmer–Lemeshow calibration, and ROC-AUC with sensitivity, specificity, and Youden's J cut-offs. Moderation analysis also will be used with simple slope analysis.

Phenotype and morphology linkages (USG/TMG/EMG).

Associations between %MHC-I and Δ CMJ will be quantified at each minute using Pearson's r. USG variables (thickness, pennation angle, fascicle length) will be analysed with the same three lenses applied to performance: (i) within-EXP time-course (rmANOVA/LMM with Tukey), (ii) responder linkage at each minute (one-way ANOVA or robust alternative; Hedges' g for P vs X), and (iii) phenotype linkage (correlations and moderation models). TMG (e.g., Dm, Tc, Tr) and EMG (e.g., normalized RMS, median frequency) follow this identical framework to ensure coherence across modalities.

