Moderation and mediation (pre-specified).

All moderators and predictors will be mean-centered; multicollinearity is checked (VIF < 5). Primary moderation models test whether (a) baseline CMJ modifies the effect of %MHC-I on Δ CMJ and (b) baseline morphology (thickness, pennation angle, fascicle length) modifies the effect of baseline CMJ on Δ CMJ. Significant interactions will be decomposed with simple slopes at -1 SD, mean, and +1 SD, with 95% CIs via nonparametric bootstrap (1,000 resamples) and publication-ready interaction plots. Exploratory mediation tests whether acute morphological change (e.g., % Δ thickness at a given minute) transmits baseline morphology effects to % Δ CMJ; indirect, direct, and total effects will be estimated by bootstrap (5,000 resamples; bias-corrected CIs) and interpreted cautiously.

Assumptions, multiplicity, and robustness.

Model diagnostics include residual normality (Shapiro–Wilk), homoscedasticity (residual–fitted patterns, Breusch–Pagan), linearity, and independence by design. Sphericity is tested for rmANOVA (Mauchly) with Greenhouse–Geisser corrections as needed. If mechanistic variables are skewed, appropriate transformations (e.g., log for EMG amplitude) are considered; otherwise we rely on LMM robustness. Multiplicity is controlled via Holm across the five between-group contrasts, FDR for correlation families, and restraint in post-hoc testing; moderation/mediation will be estimation-focused with full interval reporting and are not used to redefine the primary inference.

Reporting, visualization, and software.

We report means \pm SD with 95% CIs; between-group effects as Hedges' g; within-subject effects as d_{nZ} ; ANOVA-style effects as η^2 ; logistic results as ORs with AUC; and survival results as HRs with concordance. Figures include EMM trajectories with 95% CIs, individual waterfall plots with MDC bands, ROC curves for %MHC-I, Kaplan–Meier curves for first/peak response, interaction plots for significant moderations, and path diagrams for supported mediations. Analyses will be performed in Jamovi 2.6 and STATISTICA 13.1.

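### The five per-minute responder comparisons between EXP and CON have no specified multiplicity rule and no small-sample p-value.

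*Combined protocol and SAP*

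**What the plan says.** The opening section on objectives and endpoints lists "individual responder status at each time point" as a secondary endpoint. The data-handling section adds: "Individual response is classified using MDC". It gives no MDC value or confidence level.

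The section *Responder analyses and discrimination* sets the test: "Responder distributions (Positive/neutral/adverse) will be compared between EXP and CON at each minute using likelihood" chi-square. The minutes are those of the primary model, "Time (time effect: 4, 6, 8, 10, 12 min". No exact or small-sample alternative is mentioned.

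The section *Assumptions, multiplicity, and robustness* states: "Multiplicity is controlled via Holm across the five between-group contrasts, FDR for correlation families, and restraint in post-hoc testing". The contrasts it refers to are described under *Primary analysis and identification of the peak time*: "we estimate adjusted between-group contrasts at each minute with Bonferroni correction across the five time points". Those are contrasts of estimated marginal means of ΔCMJ, not comparisons of responder tables. The two sections differ on Bonferroni or Holm, but both correct across the five minutes.

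**The concern.** Two gaps meet here. First, five group comparisons are made on one endpoint and none of the listed rules reaches them. They are not marginal-mean contrasts or correlations, and the restraint promised for post-hoc testing sets no threshold. The same outcome at the same minutes is therefore protected when analysed as a mean and unprotected when analysed as a response category.

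Second, the likelihood-ratio chi-square relies on a large-sample approximation. In 2×3 tables with small outer cells its real error rate can be well away from the nominal level, usually above it.

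At stake is a claim that the conditioning activity changed the responder distribution at some minute. If it had no effect, that claim could still appear more often than a reader would assume from a 5% test.

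**Working it through.** The plan states no error rate, power or sample size, so there is no figure of its own to reproduce.

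**Inputs from the documents:** five minutes; three categories, hence 2 df per table; likelihood-ratio statistic; MDC cut-offs.

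**Assumptions (not in the documents):** alpha 0.05 per test; 1:1 allocation; 10–30 per arm (50 as a side check); MDC at the 95% level; category proportions and between-minute correlation as shown below.

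**Step 1. Multiplicity alone.** Five independent tests, each exactly at 5%: 1 − 0.95^5 = 22.6%. If the real per-test error is 5.6%, 1 − 0.944^5 = 25.0%. If it is 9.5%, 1 − 0.905^5 = 39.3%. Positive correlation between minutes lowers these figures.

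**Step 2. Share outside the MDC band with no group effect.** Let the error SD of one measurement be 1 and the SD of true individual change be k. Then MDC95 = 1.96 × √2, the SD of an observed change is √(2 + k²), and the share outside is 2 × [1 − Φ(1.96√2 / √(2 + k²))]. For k = 0, 0.5, 1, 1.5 and 2.5 this gives 5.0%, 6.5%, 11.0%, 17.9% and 33.5%.

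**Step 3. Simulated error of the likelihood-ratio test, no group effect.** Empty categories are dropped. The k rows use a baseline error shared across minutes. The other rows cut a latent normal variable, with correlation 0 to 0.9 between minutes.

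| Setting | Error per minute | At least one of five |
|---|---|---|
| k = 0; 12 / 20 / 30 per arm | 0.7 / 1.6 / 3.2% | 4 / 8 / 14% |
| k = 0.5; 12 / 20 / 30 per arm | 1.3 / 2.5 / 4.5% | 6 / 12 / 20% |
| k = 1.5–2.5; 12–30 per arm | about 6–9% | about 19–31% |
| 20% or more outside the band; 10–30 per arm | 5.6–9.5% | 17–39% |
| 5/90/5 (10% outside); 10–50 per arm | 2.1–8.0% | 8–34% |

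Separate runs put the lowest setting at about 3%. Runs over k = 0 to 1 spanned 3–29%. There is no sharp boundary: at about 10% outside the band, the result depends on group size. With 50 per arm and 20% or more outside, the overall figure is 20–27%.

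**Step 4. Holm on the same statistic.** With no true difference, Holm rejects something only if the smallest p-value is below 0.05/5 = 0.01. Were each test exact and independent, that would give 1 − 0.99^5 = 4.9%. With the likelihood-ratio p-value, 10–30 per arm and 20–40% outside the band, simulation gives 1.4–9.6%, above 5% in most settings.

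**Step 5. Exact p-values plus Holm.** An exact p-value falls below 0.01 with probability at most 0.01, so the family error is at most 5 × 0.01 = 5% whatever the correlation. Simulated under the MDC model with 12–30 per arm, Fisher–Freeman–Halton p-values with Holm give about 0–3%. Exact p-values without Holm would leave the Step 1 problem in place, so both parts are needed.

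**The case against.** **The multiplicity paragraph may be meant to cover this family.** There are five minutes, and the paragraph corrects five between-group contrasts. A reader might also infer the opposite, that the plan has no multiplicity control. Neither fits. The plan has a multiplicity paragraph, but the five contrasts it corrects are those of the marginal means. What stands is that no control is specified for the responder tests.

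**The test is not liberal where responders are rarest.** This is correct. With measurement error alone it is conservative at every group size tried. A reader might infer that sparse tables always inflate the error, or that a band such as 19–31% is a property of the plan. The documents support neither: that band needs k of 1.5–2.5, and they give no responder rates or sample size.

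**Ignoring the category order is a matter of preference.** This stands too. It does not raise the false-positive rate. Holm-adjusted power for a shift of 1.5 error SDs was about equal for the trend and likelihood-ratio tests (41% against 41.5% at 20 per arm; 60% against 58% at 30). An exact trend test had lower per-test power than the liberal likelihood-ratio test at 10–20 per arm. A trend test would also lose sensitivity if the conditioning activity produced more positive and more adverse responders, a pattern of interest in a study of responsiveness.

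**The endpoint is secondary.** True, and whether secondary endpoints need familywise control is debatable. But the plan already corrects ΔCMJ at these five minutes, and it gives no reason to treat its responder version differently.

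**Conclusion.** The point holds as a gap in specification for a secondary endpoint: five asymptotic tests, no assigned multiplicity rule and no small-sample p-value.

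Its size is conditional on alpha 0.05 and about 10–30 per arm. The chance of at least one false group difference is about 17–39% when an appreciable share of people (20% or more) fall outside the MDC band, and about 3–20% when only about 5–6% do. Between these, the figure depends on group size. The study's premise that individuals differ in response makes the higher range relevant, but the documents do not establish it.

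A reader might infer that the confirmatory result or the choice of peak minute is compromised. It is not: both rest on the ΔCMJ model and its corrected contrasts, and nothing in the plan lets a responder test redefine them.

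**What to change.** Keep the three-category comparison at each minute and add text to this effect: *Two-sided alpha is 0.05. P-values for the 2×3 responder tables will be exact (Fisher–Freeman–Halton or permutation) and Holm-adjusted across the five minutes.* State the MDC value and its confidence level in the same place.

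One alternative is a single repeated ordinal model with one Group test. That removes the multiplicity, but the model may be unstable if few people fall outside the MDC band. If no inference is intended, label the five comparisons descriptive and report them without p-values.

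An ordinal trend test is optional. No power gain should be promised for it, and its weakness against two-sided spread should be acknowledged.

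The cost is a sentence or two and a different test option, with no new data. The downside is a stricter threshold and some loss of power at each single minute. Before finalising, confirm that the named software gives exact p-values for a 2×3 table.

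### The responder models on %MHC-I have no penalised estimator and no rule for sparse data, so if responders are few and the true OR is not 1, the reported ORs will tend to be inflated

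*Combined protocol and SAP*

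**What the plan says.** In the combined protocol and SAP, Data handling and derived variables states "Individual response is classified using MDC", without giving the MDC. Objectives and endpoints lists "individual responder status at each time point" among the secondary endpoints, together with the association between %MHC-I and the chance of responding.

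Responder analyses and discrimination uses three response classes ("Responder distributions (Positive/neutral/adverse) will be compared between EXP and CON at each minute"). It then turns to logistic regression: "For mechanistic discrimination at specific minutes (including T^* once identified"), "we fit logistic models with %MHC-I as a continuous predictor and report ORs (95% CI"). The candidate minutes are the "post-intervention time points (4, 6, 8, 10, 12 min"). The only calibration check named is "Hosmer–Lemeshow calibration". Reporting, visualization, and software again lists ORs as the result to report from the logistic models.

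For these models, nothing is said about the estimator, the type of interval, a separation check, a minimum number of responders, how three classes become a binary outcome, or which arm or arms enter. No sample size or expected responder rate is given anywhere.

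**The concern.** An unqualified logistic model will normally be fitted by ML. When the smaller outcome class holds only a handful of people, the ML log-OR is biased away from zero. If %MHC-I separates responders from non-responders perfectly, no finite OR exists. Requiring a change beyond the MDC, dividing response into three classes and modelling single minutes all reduce the number of events per model, so sparse models are plausible.

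The plan has fallbacks elsewhere (mixed models, Greenhouse–Geisser, robust alternatives, transformations) but none here. The diagnostics under Assumptions, multiplicity, and robustness do not detect sparse-data bias or separation.

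At stake is a secondary endpoint. An inflated OR would overstate how well muscle phenotype predicts response, and an estimator chosen after seeing an infinite OR would be post hoc.

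**Working it through.** **Inputs.** From the documents: one continuous predictor, a logistic model, separate fits at chosen minutes. Not in the documents, so assumed: N (athletes in the model), responder rate, and the true OR per SD of a normally distributed %MHC-I. The plan has no figure of its own to reproduce.

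**Model.** logit P(responder) = a + ln(OR) × x, with x standard normal, fitted by ML and by Firth. ML means leave out separated samples, whose OR is infinite.

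**Set A: true OR 2.5, log-OR = ln 2.5 = 0.92.** Ranges cover different responder rates and repeated runs.

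| N | Responders | Mean ML log-OR | exp(mean) |
|---|---|---|---|
| 15 | about 4–6 | about 1.4 | 4.06 |
| 20 | about 7 | 1.2–1.3 | 3.32–3.67 |
| 30 | about 11 | about 1.1 | 3.00 |
| 60 | about 17–30 | 0.98–1.00 | 2.66–2.72 |
| 100 | – | 0.96 | 2.61 |

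The Firth mean log-OR was 0.88 to 1.00 across N=12 to 100. Firth had the lower root mean squared error in every cell and, up to N=30, gave about half as many ORs above 5.

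Median ML ORs are closer to 2.5: exp(1.08) = 2.94 at N=15 with about 4 responders, about 2.8 at N=20, about 2.7 at N=30, and 2.56 to 2.63 at N=60.

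Separation: about 7% at N=12 (about 3 responders), 1–4% at N=15, 1.2% or less at N=20, and 0.1% or less at N=30.

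**Set B: true OR 2, 20% responders, 5,000 datasets per cell.**

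| n | Expected responders | ML exp(mean log-OR) | ML median OR | Firth exp(mean log-OR) | Separated |
|---|---|---|---|---|---|
| 12 | 2.4 | 2.97 | 2.44 | 2.00 | 9.0% |
| 20 | 4 | 2.64 | 2.21 | 2.02 | 1.7% |
| 30 | 6 | 2.37 | 2.10 | 2.03 | 0.3% |
| 60 | 12 | 2.14 | 2.06 | 2.01 | 0.0% |
| 100 | 20 | 2.07 | 2.04 | 2.00 | 0.0% |

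Separation depends on the number of responders as well as on n. At n=20 with 4 expected responders it rises from 1.7% to 3.4% if the true OR is 3.

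**True OR of 1.** exp(mean log-OR) lies between about 0.98 and 1.07 in every cell, so there is no directional bias. The chance of complete separation is then 2/C(n,k) for k responders in n: 2/220 = 0.9% for 3 of 12, and 2/4,845 = 0.04% for 4 of 20.

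**Hosmer–Lemeshow.** The plan does not give the number of groups. With ten (assumed), 15 to 30 athletes means 15/10 = 1.5 to 30/10 = 3 per group, too few to be informative. The test does not address bias in the OR in any case.

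**The case against.** The strongest reply is that few responders is an assumption. That stands: with no N, MDC or responder rate, a reader might infer that the trial's ORs will be inflated or infinite, and the documents do not support this. At n=100 with 20 responders and a true OR of 2, the ML figure is 2.07, about 3–4% high (2.07/2 = 1.035), and separation is essentially nil.

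A reader might also infer that the confidence intervals are wrong. That is not supported. ML Wald 95% intervals covered the true value in 95–99% of non-separated samples. Likelihood-ratio intervals covered about 90–94%, a mild shortfall at N=15 to 20, but the plan does not say which type it will use. The point is confined to the estimate.

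Three further replies have force. Means are pulled up by a long tail, and medians are less inflated. The text says specific minutes, so a separate model at all five cannot be assumed. The OR is not the only evidence on phenotype: %MHC-I is also correlated with continuous ΔCMJ and enters moderation models, which do not have this weakness.

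Finally, Firth could be restricted to sparse cases by a trigger. That would be defensible, but using one estimator throughout avoids choosing a threshold and costs little where data are ample.

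**Conclusion.** The plan has a real gap: ORs are to be reported for a secondary endpoint with no protection against sparse or separated data. The consequence is conditional. If the true OR differs from 1, the inflation of the ML estimate is material at about N=12 to 30 in the model, small at N=60 and minor at N=100. In set A, separation is about 1–7% at N=12 to 15 and about 1% or less from N=20; it is somewhat higher where responders are fewer, as set B shows. All sizes rest on assumed N, responder rates, true ORs and a normal predictor. The confirmatory RM-ANOVA is not affected.

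**What to change.** In Responder analyses and discrimination, specify that the %MHC-I responder models are fitted by Firth penalised likelihood, with profile penalised-likelihood 95% CIs, at each minute where they are planned, including T*. State alongside this the binary coding of the three classes, the arm or arms included, and the expected number of responders per minute.

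Do not replace Hosmer–Lemeshow with a calibration slope computed in the fitting sample: it is exactly 1 by construction under ML and ordinarily above 1 after Firth shrinkage. Any calibration slope reported should be bootstrap-corrected.

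The cost is a few lines of SAP text, and a short script if Jamovi 2.6 and STATISTICA 13.1 do not offer Firth. The ORs will look less striking. With ample responders little changes: in set A at N=60, Firth gives a mean log-OR of 0.92–0.93 against 0.98–0.99 for ML in the same run.

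### The false discovery rate rule covers the %MHC-I correlations but not the %MHC-I logistic models, which address the same secondary endpoint at an unlisted set of minutes

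*Combined protocol and SAP*

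**What the plan says.** All references are to the combined protocol and SAP.

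- **Objectives and endpoints.** A secondary endpoint is the association of %MHC-I, estimated from tensiomyography, with "the magnitude, timing, and likelihood of response".
- **Data handling and derived variables.** Individual response is the change in jump height (ΔCMJ) classified against the minimal detectable change (MDC).
- **Phenotype and morphology linkages.** The association between %MHC-I and ΔCMJ "will be quantified at each minute using Pearson's r", so at five minutes (4, 6, 8, 10, 12).
- **Responder analyses and discrimination.** "For mechanistic discrimination at specific minutes (including T^* once identified"), "we fit logistic models with %MHC-I as a continuous predictor and report ORs (95% CI"), together with fit, calibration and ROC measures. Which minutes, and how many, is not stated.
- **Within-group time-course and kinetics.** For time to first and time to peak response the plan will "fit Cox proportional-hazards models to estimate hazard ratios (HR, 95% CI) and concordance (C-index"). Neither the Cox covariates nor the log-rank strata are named.
- **Assumptions, multiplicity, and robustness.** "Multiplicity is controlled via Holm across the five between-group contrasts, FDR for correlation families, and restraint in post-hoc testing". The same sentence then presents moderation and mediation as estimation and bars them from altering the primary inference. It does not mention the logistic or survival models.

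**The concern.** The plan chose to control error for the phenotype link where it is measured by correlation. At any given minute, the outcome of the logistic model is a categorised form of the ΔCMJ values that enter the correlation. One analysis falls under the FDR rule and the other under no rule. The number of logistic models is also open, so it can be settled after the data are seen.

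The study's title promises a mechanistic account of responsiveness, so the phenotype link is likely to feature in the report. As written, nothing prevents an isolated odds ratio whose interval excludes 1 from being reported as support for that link while every FDR-adjusted correlation is null. The stated error control would then not apply to the claim being made.

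**Working it through.** **The plan's own figure.** There is none to reproduce. The documents give no sample size, alpha, responder rate or error rate for these analyses.

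**Coverage, read side by side**

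| Part of the %MHC-I endpoint | Method | Minutes | Stated control |
|---|---|---|---|
| Magnitude | Pearson's r | all five | FDR |
| Likelihood | logistic OR, ROC | unlisted, includes T* | none |
| Timing | Kaplan-Meier, log-rank, Cox are the only timing methods given; %MHC-I not named | first and peak | none |

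Restraint in post-hoc testing is an intention. It sets no threshold and no order of testing.

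**Reference arithmetic.** For k independent tests at 0.05 with no true effect, the chance of at least one rejection is 1 − 0.95^k:

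- k = 1: 5.0%
- k = 2: 1 − 0.9025 = 9.75%
- k = 5: 1 − 0.7738 = 22.6%

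The minutes are positively correlated, and small-sample logistic tests do not hold 5% exactly, so simulation is needed.

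**Simulation inputs (all assumptions).** Two-sided 0.05; 20 to 40 athletes analysed; 30% responders per minute; correlation between minutes 0.3 to 0.8; %MHC-I independent of all five ΔCMJ values. Correlations are tested by Benjamini-Hochberg over five Pearson p-values. Logistic models are tested one minute at a time, unadjusted.

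**Chance of at least one false phenotype link**

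| Analysis | Likelihood-ratio | Wald |
|---|---|---|
| Logistic, 1 minute | about 6-7% | about 2-4% |
| Logistic, 2 minutes | about 10-13% | about 3-8% |
| Logistic, 5 minutes | about 19-29% | about 7-18% |

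The comparator, five FDR-controlled correlations, gives about 3-5%. When no association exists anywhere, the false discovery rate equals the chance of any rejection, so the two sets of figures can be compared directly.

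**Central case.** With 30 athletes, correlation 0.5 and five minutes, the logistic route gives about 25% (likelihood-ratio) or 15% (Wald), against about 5% for the correlations.

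**Discordant results.** With likelihood-ratio tests, an odds ratio is significant while no FDR-adjusted correlation is in about 17-26% of null trials for five minutes and 9-11% for two.

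**Sensitivity.** With 40% responders and 15 to 40 athletes, five likelihood-ratio models give 18-30% and the correlations 3.1-5.0%.

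**After the fix.** If only the FDR-adjusted correlations carry the claim, the chance of a false link is that family's 3-5%. If Holm is used across five logistic models, the first step is 0.05/5 = 0.01 and the logistic family is held at about 5%, to the extent that each test holds its own level. Keeping both families as routes to a claim gives at most 0.05 + 0.05 = 10%.

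**The case against.** **Magnitude and likelihood are different questions.** This stands in part. They are facets of one endpoint, and an effect on crossing the MDC can exist without a linear correlation. A reader might infer that the logistic models retest a single hypothesis and exist to get round the FDR rule by dichotomising. The documents do not support that: response has three classes, and the logistic coding is not given. The difference between the facets justifies reporting both, but not controlling only one.

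**The logistic models are not confirmatory.** This also stands in part. The plan uses the word confirmatory only for the repeated-measures ANOVA, and it describes the logistic output as odds ratios with intervals and AUC, with no alpha or decision rule. A reader might infer confirmatory tests at full alpha, which the text does not say. It does not call them descriptive either, although it gives moderation and mediation that kind of status in the same section.

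**The Cox and log-rank analyses may not involve %MHC-I.** This stands. A reader might infer unadjusted %MHC-I tests there, because timing is part of the endpoint and these are the only timing methods. But %MHC-I is named neither as covariate nor as stratum, and the list of figures ties it to the ROC curves and not to the Kaplan-Meier curves. No error rate is therefore attached to them here.

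**Five likelihood-ratio tests are close to the worst case.** This stands. The text says specific minutes for the logistic models but each minute for Pearson's r. Part of the likelihood-ratio excess is small-sample miscalibration: at 20 athletes and correlation 0.5 the rate is 28.0%, above the 22.6% for independent, correctly sized tests. Hence the two-minute and Wald figures above.

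**The endpoint is secondary.** True, and the primary inference is not touched.

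**Conclusion.** The concern holds for the logistic models. The plan controls error for the correlation part of the phenotype endpoint and leaves the likelihood part without adjustment, without a fixed set of minutes and without a descriptive label. This follows from the text alone.

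The size is conditional on the assumptions listed. Against 3-5% for the correlations, the chance of a false logistic link runs from about 3-8% (two minutes, Wald) to 19-29% (five minutes, likelihood-ratio). The gap is clear with five minutes under either test. With two minutes it is clear only for the likelihood-ratio test, and with one prespecified minute there is little or none.

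A reader might also infer that choosing T* from the data itself inflates the odds ratio. T* is chosen on the between-group difference, not on the %MHC-I association, and nothing calculated here shows such an effect. The gap comes from the open number of unadjusted models. The weakness limits what may be claimed on a secondary endpoint and should be corrected in the plan.

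**What to change.** In Assumptions, multiplicity, and robustness, adopt one of two rules and state it:

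1. List the minutes for the %MHC-I logistic models in advance and adjust the odds ratios across them, by Holm or by the FDR rule already used for the correlations. T* may be listed as one of them by its definition.
2. State that the logistic and ROC results are descriptive (estimates and intervals, no significance claims) and that the phenotype-response claim rests on the FDR-adjusted analysis of continuous ΔCMJ.

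The second is simpler and close to how the logistic results are already to be reported. In Within-group time-course and kinetics, name the Cox covariates and log-rank strata; if %MHC-I is among them, apply the same rule there.

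The cost is wording only: no change to data collection or to the primary analysis. The one loss is that an isolated odds ratio with p below 0.05 can no longer be presented as a finding.
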